10.6 Duration of Treatment

Participants may remain on study and continue to receive treatment in the absence of disease progression, unacceptable toxicity or withdrawal from study, intercurrent illness that prevents further administration of treatment, participant demonstrates an inability/refusal to comply with study therapy or participant withdraws from study. Patients who remain on study (receiving combination therapy, decitabine/nivolumab, or single agent nivolumab) will continue to have response assessment every 4 cycles for the first 2 years and every 6 cycles thereafter. Patients can withdraw from study at any time. Patients who proceed to allogeneic bone marrow transplant or who require a change of therapy for disease progression will come off study.

10.7 Compliance

All study related medications will be provided either subcutaneously, intracutaneously (combination of subcutaneously and intradermally) or intravenously. Patients will come for lab checks for routine monitoring and to obtain study blood work. Blood work may be done on a

PROTOCOL TITLE: I 49217 - Phase 1 CDX-1401/ Poly-ICLC +Decitabine +Nivolumab in Patients with MDS or Low Blast Count AML

± 2 day window from the day indicated on the study calendar in order to minimize subject noncompliance and with the recognition that there are sometimes commitments which cannot be re-scheduled. Patients must be seen on day 1 of each course of therapy and undergo a complete physical examination and review of toxicity.

11 PROCEDURES INVOLVED

The study-specific assessments are detailed in this section and outlined in **Appendix J** (Schedule of Procedures and Observations). Baseline and/or Screening assessments must be performed within 14 days prior to the first dose of investigational product. Any results falling outside of the reference ranges may be repeated at the discretion of the investigator. All on-study visit procedures are allowed a **window of ± 2 days** unless otherwise noted.

11.1 Participant Randomization and Registration

Eligibility of each participant will be established prior to enrollment.

Informed consent **MUST** be completed prior to receiving any study related procedures.

11.2 Baseline Evaluations

Confirmation of Eligibility: The following will be performed *within 4 weeks* prior to first dose of CDX-1401/poly ICLC (unless otherwise indicated):

- Medical history with pre-existing conditions
- Physical examination
- Vital signs (i.e., temperature, heart rate, respiratory rate, O₂ saturation, blood pressure), body weight and, height. Height collected at baseline only
- Hematology: CBC with manual differential
- Chemistry: CMP. In addition: LDH, uric acid, amylase and, lipase
- Pregnancy test urine, in females of childbearing potential (within 1 week prior to first dose of study drug)
- ECOG Performance Status
- HLA Typing: May use historical sample if available (patients who do not require HLA typing for determination of transplant eligibility will have HLA typing sent for study purposes)
- IPSS/ IPSSR (Refer to Appendix E and Appendix F for calculation instructions)
- Testing for HIV I/II Ab, HBsAg, HCV Ab+/- PCR (should be done only in patients for whom there is a concern for prior infection with one of these viral pathogens. Testing is NOT required if there is no history of infection)
- Bone Marrow Aspirate and Biopsy (with Flow Cytometry, Conventional Cytogenetics +/- FISH as appropriate). In addition:
 - Study Bone marrow samples for T-cell and methylation and gene expression studies (Section 11.11.2)

PROTOCOL TITLE: I 49217 - Phase 1 CDX-1401/ Poly-ICLC +Decitabine +Nivolumab in Patients with MDS or Low Blast Count AML

- Correlative blood sampling
- Endocrine Function Evaluation: TSH, blood glucose testing
- Concomitant Medications (List any ongoing medications with an onset within 1 week of first dose of study drug.).

The following will be performed *within 4 weeks* prior to first dose of study drug:

- Cardiac safety markers: troponin-I, BNP, CK-MB
- Electrocardiogram (ECG)
- Echocardiogram
- Urinalysis

11.3 Evaluations Performed on Day -14

- Physical examination including vital signs
- Hematology: CBC with manual differential
- Chemistry: CMP. In addition: LDH, uric acid, amylase and, lipase
- ECOG Performance Status
- Correlative blood sampling (see Section 11.11.1)
- CDX-1401/ poly-ICLC administration
- Concomitant medications
- Adverse events

11.4 Evaluations Performed on Day 1 of each Cycle

The following evaluations will be performed prior to CDX-1401/poly ICLC dosing or infusion of decitabine on Day 1 of each cycle or prior to premedication, if administered (may be performed up to 3 days prior to day of infusion), unless otherwise indicated:

- Physical examination
- Vital signs (i.e., temperature, heart rate, respiratory rate, oxygen saturation, blood pressure, body weight)
- Hematology: CBC with manual differential (Once per week of each cycle during cycles 1-4, from cycles 5 onward on day 1 and as clinically indicated)
- Hematological Improvement (HI) in MDS or low blast count AML patients treated with the combination in order to provide descriptive characteristics.
 - This will be assessed using results of blood counts on day 1 of each cycle.
- Chemistry: CMP, LDH, uric acid, amylase and, lipase (Once per week each cycle during cycles 1-4, from cycles 5 onward on day 1 and as clinically indicated)
- ECOG performance status

PROTOCOL TITLE: I 49217 - Phase 1 CDX-1401/ Poly-ICLC +Decitabine +Nivolumab in Patients with MDS or Low Blast Count AML

- Correlative blood sampling prior to study drug dosing Once per week each cycle during Cycles 1-4; from Cycle 5 onward once every 2 weeks (see Section 11.11.1)
- Decitabine administration: Day 1-Day 5 of each cycle (per standard of care for patient safety)
- Nivolumab administration: Day 1 and Day 15 of each cycle (+/-7 days)
- Concomitant Medications
- Adverse events

11.5 Evaluations Performed on Day 15 of each Cycle

- Vital signs
- Hematology: CBC with manual differential (see Section 11.4)
- Chemistry: CMP, LDH, uric acid, amylase and, lipase (see Section 11.4)
- CDX-1401/poly-ICLC administration (Day 15 of every cycle for the *first 4 cycles*: thereafter, to be given on *Day 1 of every 4th cycle* as a booster (i.e. on Day 1 of cycles 8, 12, 16, 20, 24).
- Nivolumab administration (Day 15 for *first 4 cycles*: thereafter, to be given on *Day 1 of every 4th cycle*)
- Adverse events

11.6 Evaluations Performed Specifically at End of Cycle 1

- Endocrine Function Evaluation: TSH and blood glucose
- Bone Marrow Aspirate and Biopsy (**Note:** At the end of Cycle 1, if a bone marrow aspirate is not able to be done, a bone marrow biopsy may be performed instead). In Addition:
 - Study Bone marrow samples for T-cell and methylation and gene expression studies (Section 11.11.2)
- The following cardiac safety tests will be performed at the end of Cycle 1 and as clinically indicated:
 - Cardiac Safety Markers: Troponin-I, CK-MB, BNP
 - ECG
- Adverse events
- Urinalysis

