6 MULTI-SITE RESEARCH

Refer to **Appendix K**: Instructions for Network Sites.

- The proposed project will be opened initially at Roswell Park Cancer Institute and at one potential additional site. In order to ensure that all patients are treated appropriately and in a consistent fashion we will ensure the following:
 - All sites will have the most current version of the protocol, consent document, and HIPAA authorization.
 - All required approvals (initial, continuing review and modifications) have been obtained at each site (including approval by the site's IRB of record).
 - All modifications have been communicated to sites, and approved (including approval by the site's IRB of record) before the modification is implemented.
 - All engaged participating sites will safeguard data, including secure transmission of data, as required by local information security policies.
 - All local site investigators will conduct the study in accordance with applicable federal regulations and local laws.

PROTOCOL TITLE: I 49217 - Phase 1 CDX-1401/ Poly-ICLC +Decitabine +Nivolumab in Patients with MDS or Low Blast Count AML

- All non-compliance with the study protocol or applicable requirements will be reported in accordance with local policy.
- This study will have up to two total sites including RPCI. If the study opens at a second site, the investigators will have a biweekly (i.e., once every 2 weeks) conference call to discuss the results of all patients enrolled and treated on study, otherwise the investigator will review the records of all patients enrolled at least every 2 weeks. At this review the principal investigators will review the following:
 - Problems (inclusive of reportable events).
 - Interim results.
 - The closure of the study according to the described stopping rules below
- As a phase 1 study, all AEs will be reviewed weekly by the Early Phase Clinical Trials committee at RPCI.

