	≥2 out of 6	Stop the study.

Patients may elect to discontinue nivolumab and/or vaccine after Cycle 8 and remain on study receiving single agent decitabine to allow collection of the secondary and exploratory endpoints as described above.

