10.1 Dosing and Administration

The vaccine is comprised of CDX-1401 (1 mg) given intracutaneously with 1.8 mg of Poly-ICLC. The first dose of the vaccine is given on Day -14 and then, on Day 15 of each decitabine cycle for the first 4 cycles (total of 5 vaccines). Thereafter, patients will receive a booster vaccine on Day 1 of every 4th cycle, indefinitely.

Nivolumab is to be given at a fixed dose of 3 mg/kg every 2 weeks starting on Day 1 of Cycle 1 through cycle 4 day 15. After cycle 5 nivolumab will be given as a flat dose of 480mg every 4 weeks on day 1 of each decitabine cycle (+/-7 day window). Nivolumab administration may continue on protocol until disease progression or the patient elects to discontinue nivolumab.

Decitabine/nivolumab cycles will be given on schedule every 4 weeks unless a delay is deemed clinically necessary by the treating physician/investigator. If the patient requires a delay of more than 6 weeks, they will come off study. The study schema is depicted in **Figure 3**.

Figure 3: Study Schema

For the purposes of this study, 1 cycle = 28 days and is comprised of 5 doses of IV decitabine (days 1-5), 2 doses of nivolumab during cycles 1-4 and 1 dose of nivolumab cycles 5 and above (day 1 and day 15 during cycles 1-4 or day 1 cycles 5 and above) and 1 vaccination (day 15). Protocol therapy may be given at the discretion of the treating physician within a +/-7 day window to accommodate patient’s preference, clinical judgement and schedule or outside this window after discussion with the PI.

Note: When nivolumab and decitabine are administered on the same day, decitabine is administered first, followed by nivolumab.

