11.7 Evaluations Performed on Cycle 5 Day 1 and every 4th Cycle thereafter

The following evaluations will be performed on or after day 28 of every 4th cycle of decitabine, and prior to initiation of any further therapy. In general samples and bone marrow should be done on day 29 (i.e., day 1 of a cycle) at cycles 5, 9, 13, 17, etc... of decitabine, per standard of care:

PROTOCOL TITLE: I 49217 - Phase 1 CDX-1401/ Poly-ICLC +Decitabine +Nivolumab in Patients with MDS or Low Blast Count AML

- Physical examination, including vital signs (i.e., temperature, heart rate, respiratory rate, blood pressure) and body weight
- Hematology: CBC with manual differential
- Chemistry: CMP, LDH, uric acid, amylase, lipase
- Urinalysis
- Correlative blood sampling prior to study drug dosing: once every 2 weeks (see Section 11.11.1)
- IPSS/ IPSSR (Refer to Appendix E and Appendix F for calculation instructions)
- Concomitant medication
- Adverse events
- Bone Marrow Aspirate and Biopsy (with flow cytometry, conventional cytogenetics and FISH studies as deemed appropriate by the treating physician). In addition:
 - Study Bone marrow samples for T-cell and methylation and gene expression studies (Section 11.11.2)
- Response assessment per modified International Working Group criteria for MDS (refer to Appendix D, Appendix E and Appendix F) and TTT

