11.11 Correlative Studies

11.11.1 Blood Sample Collection

Blood samples will be collected via venipuncture (green tops) for analysis of molecular markers, NY- ESO-1 cellular immune response (T-cell), (ELISPOT and ICS) and assessment of T-Regulatory cell frequency (CD4+CD25+FOXP3+ regulatory T cells) and, cell differentiation by transcription factor distribution (T-bet, GATA-3, ROR γ) and, gold-top tubes will be used for analysis of antibody response (NY-ESO-1-ELISA).

- Blood will be collected at the following time points:
 - Baseline:
 - 4, 10 mL green-top (sodium heparin) tubes ([name] lab)
 - 2, 10 mL green-top (sodium heparin) tubes (Immune Analysis Facility)
 - 1, 3.5 mL gold-top tube (Immune Analysis Facility)
 - Day -14 (prior to Cycle 1 Day 1):
 - 4, 10 mL green-top (sodium heparin) tubes ([name] lab)
 - 2, 10 mL green-top (sodium heparin) tubes (Immune Analysis Facility)
 - 1, 3.5 mL gold-top tube (Immune Analysis Facility)
 - Cycles 1-4 (once weekly):
 - 4, 10 mL green-top (sodium heparin) tubes ([name] lab)
 - 2, 10 mL green-top (sodium heparin) tubes (Immune Analysis Facility)
 - Cycle 5 and onward until end of treatment (Day 1 and Day 15) and, end of treatment:
 - 4, 10 mL green-top (sodium heparin) tubes ([name] lab)
 - 2, 10 mL green-top (sodium heparin) tubes (Immune Analysis Facility)
 - 1, 3.5 mL gold-top tube (Immune Analysis Facility)

Note: If it is determined that there is an inadequate cell number for cryopreservation and immunomonitoring at any visit, sample acquisition may be repeated at the next scheduled blood draw.

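### From cycle 5, the nivolumab lines in Sections 11.4 and 11.5 contradict the Section 10 schedule and each other

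*Combined protocol and SAP*

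**What the plan says.** The treatment section is consistent on the schedule from cycle 5. The cycle definition in Section 10.1, Sections 10.1.2 and 10.2, and the treatment calendars in 10.1.3 all put nivolumab on day 1 of every cycle, with no day 15 dose. Where these sections name the dose, it is a flat 480 mg. Appendix J note 10b puts it on the same day.

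Section 11 has two lines that differ:

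- Section 11.4 (day 1 visit list): "Nivolumab administration: Day 1 and Day 15 of each cycle (+/-7 days". No cycle limit is attached.
- Section 11.5 (day 15 visit list): "Nivolumab administration (Day 15 for *first 4 cycles*: thereafter, to be given on *Day 1 of every 4th cycle".

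The vaccine line directly above the second of these reads "thereafter, to be given on *Day 1 of every 4th cycle* as a booster" and goes on to name cycles 8, 12, 16 and so on.

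One sentence in Section 10.1 is also loosely worded: "After cycle 5 nivolumab will be given as a flat dose of 480mg every 4 weeks on day 1 of each decitabine cycle". The sentence before it gives 3 mg/kg through cycle 4 day 15, so on a literal reading cycle 5 itself is not covered. The cycle definition later in the same section removes the doubt by assigning one nivolumab dose to cycle 5 and above.

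**The concern.** These lines tell site staff when to give an investigational antibody, and they err in opposite directions. Followed alone, Section 11.5 drops three of every four infusions after cycle 4, and Section 11.4 doubles them.

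Three features of the protocol make a slip more plausible than it would otherwise be:

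- Research blood is still drawn at mid-cycle late in treatment (Section 11.11.1: "Cycle 5 and onward until end of treatment (Day 1 and Day 15"). Patients therefore attend a day 15 visit at which the unlimited line in 11.4 could be acted on.
- The summaries in Sections 9 and 19 describe nivolumab as 3 mg/kg every 2 weeks, also without a cycle limit.
- The every-4th-cycle interval has two meanings in the protocol. For the vaccine it means cycles 8, 12, 16. In Section 11.7 the assessments fall "at cycles 5, 9, 13, 17, etc... of decitabine". The nivolumab line in 11.5 names no cycles.

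At stake are dosing errors in individual patients and doubt over what counts as a deviation, since the appendix for network sites requires every deviation to be logged.

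**Working it through.** The plan gives no figure to reproduce, so the check is a count of infusions and intervals under each reading.

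**Inputs**

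- Cycle length: 28 days (Section 10.1).
- Last infusion on the two-weekly schedule: cycle 4 day 15 (Section 10.1).
- Horizon: cycles 5-8, which is 4 cycles. Section 9.1 states: "Patients may elect to discontinue nivolumab and/or vaccine after Cycle 8 and remain on study receiving single agent decitabine". Counts are therefore shown only up to that point.
- Patient: on schedule and continuing nivolumab.

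**Infusions over cycles 5-8**

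| Reading | Calculation | Infusions | Share of Section 10 |
|---|---|---|---|
| Section 10 and Appendix J note 10b | 4 cycles × 1 | 4 | 100% |
| 11.4 for day 1 visits, 11.5 for day 15 visits | 4 on day 1 + 0 on day 15 | 4 | 4/4 = 100% |
| 11.5 alone | 1 per 4 cycles | 1 | 1/4 = 25% |
| 11.4 alone | 4 cycles × 2 | 8 | 8/4 = 200% |

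The single infusion under 11.5 falls at cycle 8 if the vaccine cycles are meant, or at cycle 5 if the Section 11.7 cycles are meant. For a patient who continues nivolumab through cycle 12, the ratios are the same over the 8 cycles from 5 to 12: 8 infusions under Section 10, 2 under 11.5 alone and 16 under 11.4 alone.

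**Intervals**

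- Cycle 4 day 15 to cycle 5 day 1: 29 − 15 = 14 days. This is the intended first gap. It is also the first gap under 11.5 if cycles 5, 9, 13 are meant.
- Cycle 4 day 15 to cycle 8 day 1: 14 + 3 × 28 = 98 days. This is the first gap under 11.5 if cycles 8, 12, 16 are meant.
- Later gaps under 11.5, on either reading: 4 × 28 = 112 days, against 28 days under Section 10.

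No difference in milligrams is calculated, because neither Section 11 line states a dose.

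**Effect on the DLT assessment**

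Section 8.1 closes the DLT window on day 1 of cycle 2. The Section 10.3 hold on expansion accrual runs to cycle 4 day 29, the day on which cycle 5 would begin. The conflicting instructions start at cycle 5, so they fall outside the DLT window.

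**The case against.** The strongest reply is that the protocol already settles the schedule. Section 10 is the treatment section and states the rule several times. Section 11 refers the reader to Appendix J, where note 10b gives the correct days. Sections 11.4 and 11.5 are visit checklists, and nobody could order a cycle 5 infusion from them because they carry no dose. The 480 mg figure always appears beside the four-weekly interval.

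The extreme counts also need an unnatural use of the lists. The 25% figure has staff taking day 1 dosing from the day 15 list. The 200% figure has them taking day 15 dosing from the day 1 list while ignoring the day 15 list, which stops day 15 infusions after cycle 4.

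Oversight limits any error further. If only one site is open, Section 6 says "the investigator will review the records of all patients enrolled at least every 2 weeks"; with two sites, the investigators confer every 2 weeks. At most 18 evaluable patients are enrolled.

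All of this stands, and it bounds the practical risk. It does not make the two lines correct. They are complete sentences in current text, they disagree with each other on both visit days, and one of them misstates the day 1 interval outright. That the right answer can be found elsewhere is a reason to expect few errors, not a reason to leave the instructions as they are.

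**Conclusion.** The inconsistency is real and should be corrected. From cycle 5, Section 11.5 understates the nivolumab schedule and Section 11.4 overstates it; the ratios assume that one line is followed alone. Section 11.5 probably picked up the booster wording from the line above it, but that is an inference.

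The intended schedule is not in doubt. The DLT assessment and the primary DLT analysis are unaffected, and no effect on a particular immune analysis is claimed. The loose wording in Section 10.1 is a minor point that the same section resolves.

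**What to change.** Three wording changes are needed:

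1. Section 11.5, nivolumab line: *Day 15 for cycles 1-4; from cycle 5, 480 mg on Day 1 of every cycle.*
2. Section 11.4, nivolumab line: limit the day 15 infusion to cycles 1-4.
3. Section 10.1: start the flat dose *from cycle 5* rather than after it.

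An optional tidy-up in Appendix J would bring the nivolumab row into line with note 10b, and the vaccine mark in the cycle 5 column into line with note 10 (cycles 8, 12, 16 and so on).

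The cost is a wording amendment. Design, sample size and analysis do not change.

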11.7 Evaluations Performed on Cycle 5 Day 1 and every 4th Cycle thereafter

The following evaluations will be performed on or after day 28 of every 4th cycle of decitabine, and prior to initiation of any further therapy. In general samples and bone marrow should be done on day 29 (i.e., day 1 of a cycle) at cycles 5, 9, 13, 17, etc... of decitabine, per standard of care:

PROTOCOL TITLE: I 49217 - Phase 1 CDX-1401/ Poly-ICLC +Decitabine +Nivolumab in Patients with MDS or Low Blast Count AML

- Physical examination, including vital signs (i.e., temperature, heart rate, respiratory rate, blood pressure) and body weight
- Hematology: CBC with manual differential
- Chemistry: CMP, LDH, uric acid, amylase, lipase
- Urinalysis
- Correlative blood sampling prior to study drug dosing: once every 2 weeks (see Section 11.11.1)
- IPSS/ IPSSR (Refer to Appendix E and Appendix F for calculation instructions)
- Concomitant medication
- Adverse events
- Bone Marrow Aspirate and Biopsy (with flow cytometry, conventional cytogenetics and FISH studies as deemed appropriate by the treating physician). In addition:
 - Study Bone marrow samples for T-cell and methylation and gene expression studies (Section 11.11.2)
- Response assessment per modified International Working Group criteria for MDS (refer to Appendix D, Appendix E and Appendix F) and TTT

11.8 Evaluations Performed at End of Treatment

The following evaluations will be performed \pm 4 days from day 29 of the last cycle of decitabine, and prior to initiation of any further therapy:

- Physical examination and vital signs
- Hematology: CBC with manual differential
- Chemistry: CMP
- ECOG Performance Status
- IPSS/ IPSSR (Refer to Appendix E and Appendix F for calculation instructions)
- Bone marrow aspirate and biopsy (with flow cytometry, conventional cytogenetics and FISH studies as deemed appropriate by the treating physician). In addition:
 - Bone marrow samples for T-cell and methylation and gene expression studies (Section 11.11.2)
- Blood sample for immune correlates (Section 11.11.1)
- Concomitant medications
- Adverse events
- Response assessment per modified International Working Group criteria for MDS (refer to Appendix D, Appendix E and Appendix F) and TTT

PROTOCOL TITLE: I 49217 - Phase 1 CDX-1401/ Poly-ICLC +Decitabine +Nivolumab in Patients with MDS or Low Blast Count AML

11.9 Post-Treatment Follow-Up Evaluations

Follow-up safety evaluations will occur 30 days (± 3 days), 60 days (± 3 days), 90 days (± 3 days), and 180 days (± 3 days) after last dose of study drug or until resolution of any drug-related toxicity (telephone contact is acceptable). Patients will be asked to report any possible auto-immune reactions (including rashes, skin changes, new symptoms of arthritis or other auto-immune phenomena) in order to capture possible late manifestations of auto-immunity.

- Concomitant medications
- Adverse events
- Survival Status: Disease progression/change in treatment

Patients remaining on study for ≥ 2 years will have a bone marrow biopsy performed every 6 months (± 2 months) per standard of care follow up.

